--	---

	

• Has received an IMP within the 30 days prior to Visit 1.

• Has any other clinically significant disease or disorder (including seizure disorder) that, in the opinion of the investigator, may put the patient, other patients, or site staff at risk because of participation in the trial, influence the interpretation of trial results, or may affect the patient's ability to take part in the trial.

• Has any abnormalities identified following a physical examination, clinical laboratory, serology, or other applicable screening procedures that, in the opinion of the investigator, would jeopardize the safety of the patient or the conduct of the study if he or she took part in the trial.

• Has any history of suicidal behavior in the 5 years prior to Visit 1 or a score of 3, 4, or 5 on the C-SSRS in the month prior to Visit 1.

• Has donated blood during the 3 months prior to Visit 1 and is unwilling to abstain from donation of blood during the trial.

• Has been previously randomized into this trial.

• Has any known or suspected history of alcohol or substance abuse (including opiate abuse) or dependence within 1 year prior to Visit 1.

• Currently using an illicit drug or current nonprescribed use of any prescription drug.

• Has a history of psychiatric or neurologic disorder that, in the opinion of the investigator, may interfere with trial participation, data interpretation, or conduct of trial procedures.

• Has a history of severe psychiatric disorder that may be exacerbated by the use of a cannabinoid-containing product.

• Has any planned clinical interventions or intends to change any or all medications that may have an effect on spasticity or MS during the trial.

• Currently taking drugs that are solely metabolized by UGT1A9 and UGT2B7.

• Currently taking strong CYP3A4 inducers (e.g., rifampicin, carbamazepine, phenytoin, phenobarbital, St John's Wort).

Criteria for Withdrawal	
The patient must be withdrawn from the trial if any of the following apply:
 

• Administrative decision by the investigator, GW Pharma Ltd, or regulatory authority

• Withdrawal of patient consent

• Lost to follow-up

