	
time each day in a consistent manner in relation to food consumption. Morning and evening doses should be administered around the same time within 30 minutes after starting a snack or meal. Patients will gradually titrate their daily dose to the maximally acceptable dose, balancing efficacy and tolerability, or to a maximum number of 12 sprays/day. During the titration phase, there should be an approximately 15-minute interval between sprays.
 
Patients should complete titration within approximately 14 days of their first dose of IMP in each treatment period and should continue at the same dose level achieved at the end of titration phase (i.e., their daily optimized dose) <math>\pm</math> 1 spray/day divided into a morning dose and an evening dose for the remainder of the treatment period.
 
Once a stable daily dose has been reached, patients should gradually decrease the interval between sprays to a target interval of approximately 1 minute between sprays.
 
Throughout each treatment period, patients will be advised to administer IMP at approximately the same time each day in a consistent manner in relation to food consumption.

Control Arm	All patients enrolled in the trial will receive both nabiximols and placebo during the 2-way crossover treatment period.
Procedures	
Assessments/procedures at the trial site include the following:
 

• Informed consent, demographics, previous cannabis use, medical history, electronic diary training, and blood THC test (Visit 1)

• Eligibility check and urine drug screen (including THC) (Visits 1 and 2 [predose])

• Randomization and IMP dosing training (Visit 2 [predose])

• Concomitant medications review, AE review, and vital signs (when at the trial site) measurement (Visits 1 through 10)

• Physical examination (including height measurement at Visit 1 only), 12-lead ECG, and clinical laboratory blood sampling (hematology and biochemistry) (Visits 1, 5, and 9)

• Examination of oral mucosa (Visits 1, 2 [predose], 4, 5, 6 [predose], 8, 9, and 10)

• Body weight measurement (Visits 1, 2 [predose], 6 [predose], and 10)

• Dipstick urinalysis and serum pregnancy test (if appropriate) (Visits 1 and 10)

• Urine pregnancy test (if appropriate) (Visits 2 and 6 [predose])

• PK blood sampling (IMP) at distinct time points (Visits 2, 4, 5, 6, 8, and 9)

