	

• MAS assessment (Visits 1, 2 [predose and at 3 hours <math>\pm</math>15 minutes postdose], 5 [3 hours <math>\pm</math>15 minutes after the first spray of the morning dose], 6 [predose and at 3 hours <math>\pm</math>15 minutes postdose], and 9 [3 hours <math>\pm</math>15 minutes after the first spray of the morning dose])

• MSSS-88 assessment (Visits 5 and 9)

• T25FW test (Visits 2 [predose], 5, 6 [predose], and 9)

• C-SSRS assessment (Visits 1, 2 [predose], 4, 5, 6 [predose], 8, 9, and 10)

• IMP dosing at the investigational site (Visits 2, 5, 6, and 9)

• IMP dispensing (Visits 2, 4, 6, and 8)

• IMP collection and compliance review (Visits 4, 5, 8, and 9)

 
Additional procedures to screen for the presence of or immunity against infectious diseases may be conducted according to local guidance and policy. In cases where patients are not able to attend study visits due to the presence of an infectious disease or other transmissible condition, the investigator will discuss with the Sponsor potential mitigation approaches.

Statistical Considerations	The Lower Limb Muscle Tone-6 (LLMT-6) will be derived as the average of individual MAS transformed scores (of left knee flexors, right knee flexors, left knee extensors, right knee extensors, left plantar flexors, and right plantar flexors) for each patient. The change from baseline in LLMT-6 in treatment period 1 for each patient will be derived as LLMT-6 at Day 21 minus LLMT-6 at Day 1 predose and the change from baseline in LLMT-6 in treatment period 2 for each patient will be derived as LLMT-6 at Day 51 minus LLMT-6 at Day 31 predose. The primary estimand involves the mean treatment

[figure not shown]

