### **6.1 Inclusion Criteria**

#### *Screening (Visit 1)*

For inclusion in the trial, patients must fulfill ALL of the following criteria:

- 6.1.1 Male or female, aged 18 years or above.
- 6.1.2 Willing and able to give informed consent for participation in the trial (see [Section 15.2](#)).
- 6.1.3 Willing and able (in the investigator's opinion) to comply with all trial requirements.
- 6.1.4 Has had a diagnosis with any disease subtype of MS, by revised 2017 McDonald criteria, for at least 12 months prior to Visit 1 and is expected to remain stable for the duration of the trial.
- 6.1.5 Has an MAS untransformed score of at least 2 in 2 or more of 6 muscle groups (right knee flexors, left knee flexors, right knee extensors, left knee extensors, right plantar flexors, or left plantar flexors) at Visit 1.
- 6.1.6 If currently receiving approved anti-spasticity therapy, it must be with a stable dosing regimen for at least 30 days prior to Visit 1. The patient must be willing to maintain the same antispasticity medication and not plan to initiate a new course of physiotherapy for the duration of the trial.
- 6.1.7 If currently receiving an approved MS disease-modifying therapy, it must be at a stable dose for at least 3 months prior to Visit 1 and is expected to remain stable for the duration of the trial.
- 6.1.8 If currently receiving dalfampridine or fampridine, it must be at a stable dose for at least 3 months prior to Visit 1 and is expected to remain stable for the duration of the trial.
- 6.1.9 Willing to allow the responsible authorities to be notified of participation in the trial, if mandated by local law.
- 6.1.10 Willing to allow his or her primary care practitioner (if he or she has one) and/or treating neurologist (if he or she has one) to be notified of participation in the trial, if the primary care practitioner/treating neurologist is different from the investigator.

*Additional Inclusion Criteria at Randomization (Visit 2)*

Patients are eligible for randomization in the trial if, in addition to continuing to meet the Screening (Visit 1) inclusion criteria, they also meet the following criterion prior to Visit 2 (Day 1):

6.1.11 Completed at least 5 of 7 days of their electronic diary reporting during the 7 days immediately preceding Visit 2 (Day 1).

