6.2.14 Has moderately impaired hepatic function at Visit 1, defined as serum alanine aminotransferase (ALT) or aspartate aminotransferase (AST) > 2 × upper limit of normal (ULN). All measurements will be performed singly and can be repeated once, if any are outside the reference range but not considered clinically significant.

6.2.15 Male and fertile (i.e., after puberty unless permanently sterile by bilateral orchectomy) unless willing to ensure that he uses male contraception (condom or vasectomy) or remains sexually abstinent during the trial and for 3 months thereafter.

6.2.16 Female and of childbearing potential (i.e., following menarche and until becoming postmenopausal for ≥ 12 consecutive months unless permanently sterile by hysterectomy, bilateral salpingectomy, or bilateral oophorectomy) unless willing to ensure that she uses a highly effective method of birth control (e.g., intrauterine device/hormone-releasing system, bilateral tubal occlusion, vasectomized partner, or sexual abstinence) during the trial and for 3 months thereafter. Patients using combined hormonal methods or a progestogen-only pill or injection or implant should use an additional barrier method such as a condom or diaphragm during the trial and for 3 months thereafter (see [Section 9.2.2](#)).

6.2.17 Female and pregnant (positive pregnancy test at Visit 1 or Visit 2), lactating, or planning pregnancy during the course of the trial or within 3 months thereafter.

6.2.18 Has received an IMP within the 30 days prior to Visit 1.

6.2.19 Has any other clinically significant disease or disorder (including seizure disorder) that, in the opinion of the investigator, may put the patient, other patients, or site staff at risk because of participation in the trial, may influence the interpretation of trial results, or may affect the patient's ability to take part in the trial.

6.2.20 Has any abnormalities identified following a physical examination, clinical laboratory, serology, or other applicable screening procedures that, in the opinion of the investigator, would jeopardize the safety of the patient or the conduct of the study if he or she took part in the trial.

- 6.2.21 Has any history of suicidal behavior in the 5 years prior to Visit 1 or a score of 3, 4, or 5 on the C-SSRS in the month prior to Visit 1.
- 6.2.22 Has donated blood during the 3 months prior to Visit 1 and is unwilling to abstain from donation of blood during the trial.

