#### **9.1.1 Screening (Visit 1 [Days -28 to -1])**

Informed consent (see [Section 9.2.1](#)) must be obtained from the patient prior to beginning any trial-related procedures.

The following assessments/procedures will be performed:

- Eligibility check ([Section 6](#))
- Demographics ([Section 9.2.3](#))
- Previous cannabis use ([Section 9.2.4](#))
- Medical history ([Section 9.2.5](#))
- Electronic diary training ([Section 9.2.14.1](#))
- Concomitant medications review ([Section 9.2.6](#))

- AE review ([Section 9.2.17](#))
- Physical examination (including height measurement; [Section 9.2.7](#))
- Oral mucosa examination ([Section 9.2.8](#))
- Body weight measurement ([Section 9.2.9](#))
- Vital signs measurement ([Section 9.2.10](#))
- 12-lead ECG ([Section 9.2.11](#))
- Clinical laboratory blood sampling (hematology and biochemistry) ([Section 9.2.12](#))
- Dipstick urinalysis ([Section 9.2.12](#))
- Urine drug screen (including THC) ([Section 9.2.12](#))
- Serum pregnancy test (if appropriate) ([Sections 9.2.2 and 9.2.12](#))
- Blood THC test ([Section 9.2.12](#))
- MAS assessment ([Section 9.2.15.1](#))
- C-SSRS assessment ([Section 9.2.15.3](#))

The investigator should review the laboratory results as soon as these become available. If the results show that a patient is ineligible, the patient will fail screening.

Following Visit 1, there will be no changes in the dosing regimen of the patient's current oral MS antispasticity medications (if any).

Patients who satisfy all of the inclusion criteria and none of the exclusion criteria specified in [Section 6](#) will enter a baseline period of at least 7 days prior to Visit 2, during which they will be required to take their oral antispasticity medication (if any) and complete an electronic daily diary to record their 11-point NRS spasticity score, spasm count, and use of antispasticity medications once daily, around the same time each day, preferably in the evening before retiring to sleep.

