#### **9.1.2.1 Visit 2 (Day 1)**

Patients will return to the site in the morning of Day 1 when eligibility will be confirmed and patients will be randomized.

The following assessments/procedures will be performed on Day 1 predose:

- Eligibility check
- Concomitant medications review
- AE review
- Examination of oral mucosa
- Body weight measurement
- Vital signs measurement
- Urine drug screen (including THC)
- Urine pregnancy test (if appropriate)
- Randomization ([Section 7.2](#))
- PK blood sampling for IMP ([Section 9.2.12.1](#))
- MAS assessment
- T25FW test ([Section 9.2.15.4](#))
- C-SSRS assessment
- IMP dosing training ([Section 9.2.14.3](#))
- IMP dispensing

Following predose assessments and after IMP dosing training and dispensing, site staff will observe dosing by the patient and verify that IMP was correctly administered. Patients will administer a single dose of IMP with a standardized snack containing at least 300 kcal (of which approximately 30 kcal is composed of fat) at the trial site under the supervision of site staff.

The following assessments/procedures will be performed 2 to 4 hours postdose:

- MAS assessment (3 hours  $\pm$ 15 minutes postdose)
- AE review
- Vital signs measurement
- PK blood sampling for IMP ([Section 9.2.12.1](#))

The patient will be provided dosing instructions and advised to contact the investigational site when in doubt about changes in the daily dose of IMP. The patient will be instructed to record IMP doses administered in the patient electronic diary.

The exact time of PK blood sampling and the time of the patient's snacks and meals should be recorded.

Following Visit 2, patients will titrate their daily dose of IMP for approximately 14 days until they achieve an optimized dose with an approximately 15-minute interval between sprays; patients should divide doses greater than 1 spray/day into a morning dose and an evening dose. Administration of the morning and evening doses of IMP should be maintained around the same time each day in a consistent manner in relation to food consumption, i.e., within 30 minutes after starting a snack or meal.

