### **9.2.15.3 Columbia-Suicide Severity Rating Scale**

The definitions of behavioral suicidal events used in this scale are based on those used in the Columbia Suicide History Form. Questions are asked on suicidal behavior, suicidal ideation, and intensity of ideation. At Screening (Visit 1), questions will be in relation to lifetime experiences (baseline). Questioning at all subsequent visits will be in relation to the last assessment (since last visit).

The C-SSRS is to be administered by the investigator or his or her qualified designee at Visits 1 through 10 as indicated in the schedule of assessments (see [Appendix 1](#)); “qualified designee” is defined as anyone who has completed the C-SSRS training within the past 2 years or has continually administered C-SSRS assessments throughout the trial since obtaining the training certificate. The survey should be completed by the same assessor, where possible, throughout the trial. Assessments will be conducted only if patients are capable of understanding and answering the questions, in the investigator’s opinion.

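### The suicidality exclusion stops at Visit 1, so type 3 to 5 ideation or suicidal behaviour arising afterwards and reported on the Visit 2 pre-dose C-SSRS does not bar randomization

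*Protocol*

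**What the plan says.** Protocol 6.2.21 begins: "Has any history of suicidal behavior in the 5 years prior to Visit 1 or a score of 3, 4, or 5". The synopsis carries the same criterion, and in both places the ideation limb is "a score of 3, 4, or 5 on the C-SSRS in the month prior to Visit 1". Both look-back windows end at Visit 1.

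After Visit 1 the patient "will enter a baseline period of at least 7 days prior to Visit 2" (Protocol 9.1.1), within a screening period of up to 28 days. At Visit 2, "Patients will return to the site in the morning of Day 1 when eligibility will be confirmed and patients will be randomized" (Protocol 9.1.2.1). The synopsis schedules "Eligibility check and urine drug screen (including THC) (Visits 1 and 2 [predose" and also "C-SSRS assessment (Visits 1, 2 [predose], 4, 5, 6 [predose], 8, 9, and 10", so an eligibility check and a C-SSRS both fall before the first dose. On the recall window, Protocol 9.2.15.3 says: "Questioning at all subsequent visits will be in relation to the last assessment (since last visit".

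The entry rule at randomization (Protocol 6.1) is that patients are eligible if, "in addition to continuing to meet the Screening (Visit 1) inclusion criteria, they also meet the following criterion prior to Visit 2 (Day 1". The one criterion added there is electronic diary completion. SAP 12.7.5.3 likewise places the assessment of suicidality eligibility at the Screening visit.

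Protocol section 10 and the synopsis withdrawal criteria make it mandatory to stop study drug for suicidal behaviour, or ideation of type 4 or 5, during the treatment period. Type 3 is not named.

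**The concern.** The protocol sets a fixed suicidality threshold for entry and then collects the same instrument again on the morning of randomization. The threshold is tied to a window that has already closed, so the second form has no defined consequence for entry. A patient could report new type 3, 4 or 5 ideation, or suicidal behaviour, since Visit 1 and still satisfy every criterion that does not depend on investigator opinion or on some other diagnosis.

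What is at stake is patient safety on dosing day. After a single supervised spray, patients titrate at home towards a maximum of 12 sprays a day (Protocol 8.1.2). The Day 8 telephone contact covers adherence, titration, concomitant medication and adverse events, but not the C-SSRS (Protocol 9.1.2.2). The next scheduled C-SSRS is Visit 4, Day 15, after the roughly 14-day titration. There is no data safety monitoring committee (Protocol section 14), and the SAP lists suicidal ideation and behaviour as an adverse event of special interest (Appendices 11 and 12). The Visit 2 form is thus the last scheduled suicidality check before home titration.

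There is also a data cost. A patient who is randomized and then stops study drug in Period 1 contributes no collected Period 2 data (SAP Table 9.1-2 and 12.5.2.1.1). Exclusion before randomization avoids that loss.

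**Working it through.** No sample size, power or error-rate figure bears on this point. The check compares rules, with one interval to compute.

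**Interval covered by the Visit 2 form.** The minimum is the baseline period of at least 7 days (Protocol 9.1.1). The maximum is Day -28 to Day 1. There is no Day 0 (SAP 10.1.2), so the gap is 1 - (-28) - 1 = 28 days. The form therefore covers 7 to 28 days, all after the 6.2.21 windows close.

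**Rules applied to an event arising in that interval and reported at Visit 2 pre-dose:**

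| Result at Visit 2 | Exclusion 6.2.21 | Added Visit 2 criterion | Mandatory stop of study drug |
|---|---|---|---|
| Type 3 ideation | Does not apply | Diary only | Does not apply: type 3 not named |
| Type 4 or 5 ideation | Does not apply | Diary only | Only if Visit 2 pre-dose is in the treatment period |
| Suicidal behaviour | Does not apply | Diary only | Only if Visit 2 pre-dose is in the treatment period |

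**Does the Visit 2 eligibility check close the gap?** No. Applying 6.2.21 again at Visit 2 applies the same window ending at Visit 1. Where the protocol wants a Visit 2 result to count, it says so: blood pressure (6.2.12) and pregnancy (6.2.17) both name Visit 1 or Visit 2. 6.2.21 does not, although its instrument is also repeated.

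**Is Visit 2 pre-dose in the treatment period?** The documents point both ways. The heading of Protocol 9.1.2 puts Visits 2 to 5 in Treatment Period 1. SAP 10.1.1 runs screening up to the first study drug intake on Day 1. Even on the protocol's reading, the rule stops study drug; it does not bar randomization.

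**Order of procedures.** In the 15-item pre-dose list in Protocol 9.1.2.1, randomization is item 9 and the C-SSRS is item 13. The list is not stated to be sequential, so this does not show that the form comes second. It shows only that nothing requires it to come first.

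**Scope.** An event that falls within the 6.2.21 look-back but is disclosed only at Visit 2 still meets 6.2.21. The gap concerns events after Visit 1.

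**The case against.** The strongest reply has three parts.

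First, the protocol itself places Visit 2 in Treatment Period 1, and a SAP period definition written for analysis should not narrow a protocol safety rule. On that view behaviour and types 4 and 5 at Visit 2 already trigger a mandatory stop. This is a reasonable reading and may be the better one. It would prevent the dose but not randomization, and it leaves type 3 untouched.

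Second, leaving type 3 to judgement may be deliberate. Study drug is not stopped for type 3 during treatment, and SAP 10.23 treats scores of 4 to 5 as serious while allowing a baseline of 0 to 3. That shows type 3 is tolerated once a patient is on treatment. It does not explain why the same answer excludes at Visit 1 but has no set consequence when given on dosing day before the first spray.

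Third, discretion is close at hand. The investigator or a trained designee administers the form. Exclusions 6.2.19, 6.2.20 and 6.2.26 allow exclusion on the investigator's opinion, 6.2.27 may catch a patient with a history of severe psychiatric disorder, and section 10 permits withdrawal by the investigator's administrative decision. All of this stands, and it lowers the risk. But the protocol set a fixed threshold at Visit 1 despite having those clauses, so discretion alone is a weaker standard for the same finding at Visit 2.

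It is also true that no incidence is available and that no further patient will be enrolled in this trial unless it restarts.

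**Conclusion.** The concern holds. For events arising in the 7 to 28 days between Visit 1 and Visit 2, none of the results that exclude at Visit 1 (behaviour, types 3, 4 and 5) is a mandatory exclusion at Visit 2. Type 3 triggers no mandatory suicidality action at all on the Visit 2 form. Behaviour and types 4 and 5 trigger a mandatory stop of study drug on one of two available readings of the treatment period, and bar randomization on neither.

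The conclusion rests on the text of the criteria and is limited to mandatory suicidality rules; investigators keep their discretion. How many patients would be affected cannot be estimated from the documents. This is a cheap safety improvement that should be made wherever these criteria are used again. It does not affect the validity of the efficacy analysis.

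**What to change.** Add to 6.2.21 and the matching synopsis criterion a further limb: any suicidal behaviour, or a C-SSRS score of 3, 4 or 5, since Visit 1 as reported on the Visit 2 pre-dose form. In Protocol 9.1.2.1, require that form to be completed and reviewed before randomization.

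The cost is small. No assessment or visit is added, because the form is already scheduled before dosing. The downsides are possibly a few more screen failures, moving the C-SSRS ahead of randomization in the Visit 2 workflow, and a protocol amendment with the notifications and approvals described in Protocol 16.1. Because the SAP addendum (section 6.0) records that enrollment was halted on 9 November 2022, the benefit is confined to a restart or a later protocol built on this text.
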